Longitudinal studies reveal early life markers of poor health outcomes over the lifespan that include low birth weight, irritable temperament in early childhood and poor frustration tolerance, parental stress, attentional deficits and even increased blood pressure. These conditions can be quantified and we propose to use such measures in the development of longitudinal studies on the interactions between prenatal and postnatal environmental conditions in predicting health outcomes. **Specifically, we will investigate influences of the early environment (prenatal and early neonatal) on neuropsychological development. Our focus for the study of postnatal environment is on maternal well-being and mother-infant interactions. Hence our measures include not only functional assessment of the offspring, but also measures focusing on the mother. We feel that this study will provide a crucial basis for the development of focused, early intervention programs.**

Adverse Perinatal Environment: Development of Disease

There is a dramatic increase in the risk for coronary heart disease, obesity and diabetes (metabolic syndrome) among individuals who were small for gestational age, a condition that implies some measure of intrauterine growth retardation (IUGR) and adverse fetal environment ([name] 2001; Barker 2002; Seckl et al. 1999). The health risk appears linked to the programming effects on gene expression, especially that of hepatic genes. The conditions of risk associated with impoverished fetal life are not restricted to cardiovascular or metabolic disease. Adverse intrauterine environment has also been linked to neurodevelopmental disorders. Both prematurity and IUGR

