Participants. Our approach will be to develop a human cohort derived from a study already nearing completion in Montreal (The Montreal Prematurity Study funded by the March of Dimes; PI: [name]). [name] is a collaborator on the MAVAN project, and Drs. [name] and [name] are collaborators on the Prematurity Study. The Prematurity study involves measures of psychosocial stress, nutrition, and family and community living conditions as predictors of gestational length, which is the outcome measure in this project. This project will recruit 5000 women at 13-15 weeks gestation, of which approximately 4000 have been recruited and will have given birth before the start of our project, leaving a population of 1200 potential subjects. Currently, 100 women each month are assessed at 24-26 weeks gestation. There is currently in place an infrastructure for follow-up of women from the Montreal Prematurity Study.

The cohort for the current MAVAN project will be derived from the same population used in the Prematurity Study. In essence the MAVAN Project will serve as a follow-up study derived from the Prematurity Study focusing on a substantially smaller population. The strategy for the MAVAN Project is to take advantage of the multivariate assessment of prenatal adversity in The Montreal Prematurity Study. We will follow infants born at normal weight (controls, n= 120; 3000-3500 g at birth) and low-

birth weight babies exhibiting evidence for intrauterine growth retardation (IUGR, n= 120; 2200-2750 g at birth). These groups are based on the recently published Canadian standards for fetal growth (Kramer, M. S., R. W. Platt, S. W. Wen, K. S. Joseph, A. Allen, M Abrahamowicz, B. Blondel, and G. Bréart. 2001. "A new and improved population-based Canadian reference for birth weight for gestational age." *Pediatrics* 108:), which indicates that the birth weight of 2,750 g represents the 10th percentile, with a weight of 3750 g at the 70th percentile. Our intent is to avoid extreme cases of growth retardation (i.e., < 2,200 g). All babies in this study will be born at > 37 weeks gestation to avoid the complication of prematurity and growth restriction. We will recruit two cases for each case (i.e., two infants of normal birth weight for each infant that is small for gestational age).

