Finally, we mention the possibility of brain imaging in children. However, the details of the procedure have not yet been finalized and would pertain only to the children of 36 months of age. Please note that we will conduct imaging only in unanesthetized subjects. Under no conditions would we consider the possibility of any sedative agent. The Montreal Consortium for Brain Imaging Research, of which [name], [name], [name], and [name] are members and [name] the Director, is the lead site for the NIH Developmental Brain Mapping project. The lead site for neuroimaging (structural MRI) of younger children is at Washington University in St. Louis. To date, this site has imaged ~150 children using no anesthetic or sedative and is the most experienced site in the world. We have had extensive consultation with this team and the information provided suggested that our original plan to image infants was unlikely to be feasible with the current CIHR budget. In contrast, they report remarkable success with children above 24 months (i.e., >70%), especially when children are prepared for scanning with experience in a Mock Scanner, which simulates the imaging conditions (noise, confinement, etc.) with the exception of the actual

magnets. The Douglas Hospital Research Centre will be purchasing such a scanner over the next 8 months.

General procedure

Six-month home interview: First visit (90 minutes)

Mother

1. Questionnaires (Time required for completion is approximately 90 minutes)

1.1 Stress:

1.1.1. Perceived Stress Scale. Maternal stress measures are assessed at 6 and 12 months postpartum. Perceived stress is assessed using the short form of the Perceived Stress Scale (4 items) (Cohen et al. 1983). The short form has an internal consistency of .72 (coefficient alpha) and two month test-retest reliability of .55.

1.1.2. The Parental Stress Scale, (Berry and Jones, 1995) is an 18-item scale, which has good internal reliability (alpha = .83) and good 6-week test-retest stability (.81). This scale is much shorter than the Parenting Stress Index and is especially useful when samples include parents whose child does not have a developmental disability.

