1.1.4 Chronic stressors are assessed via measures of money problems, food security, housing problems, work stress, negative interactions with others and conjugal violence. The money problem questions were drawn from the Daily Hassles Scale (Kanner et al., 1981). Each woman is asked if, since the beginning of their pregnancy, they have lacked money to: (1) pay for housing, (2) pay for electricity, hot water or heating, (3) buy food, (4) buy prescription medications, (5) buy or pay for anything else that she or her family needs.

1.1.5. Work stress is assessed with a 13-item abbreviated version (Fenster et al., 1995) of the Karasek Job Content Questionnaire (Karasek et al., 1986). This measure includes four items on job demands and five items on job control as well as four items on social support at work.

1.1.6. The negative interactions measure asks the first name and relationship of each person with whom the woman can expect to have unpleasant disagreements or to be made angry or upset. The woman also indicates the number of times in the past two weeks that she has had a disagreement with each of these people. This is taken from the Arizona Social Support Interview Schedule (ASSIS) (Barrera M., 1981).

1.1.7. The Marital Strain Scale (Pearlin et al., 1978) is used to assess chronic stress with one's romantic partner. The 9 items represent the three items with the highest factor loadings for each of the three factors contributing to the measure of marital strain. In addition, the Abuse Assessment Screen is used to assess conjugal violence. This five-item instrument assesses the frequency, severity, perpetrator, and body sites of injury (McFarlane et al., 1992; Parker et al., 1993).

1.1.8 Lazarus and Folkman's measure of primary appraisals (of challenge, threat, and centrality) is administered (14 items) (Folkman and Lazarus, 1985).

1.1.9 Reactive responding. This is a 9 items scale that we obtained from [name] based on her work with the MacArthur Network on socioeconomic status and health. The idea is that those who have experienced chronic stress develop a hypervigilant response style to ambiguous environmental stimuli.

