Although there are laboratory-based observational procedures for assessing infant temperament (e.g., Goldsmith & Rothbart, 1996) these are labour intensive and therefore not as widely used as parent report instruments. The Infant Behavior Questionnaire, Revised Version (IBQ, Garstein and Rothbart, 2003) is completed at 6 and 12 months and the toddler version at 36 months. This is a widely used parent-report measure of infant temperament. The items represent 14 scales but factor analysis reveals three primary factors: a) impulsivity, b) negative affectivity and c) effortful control. We chose this instrument, partly because of interest in impulsivity as a key outcome variable and partly because this measure is well researched and has internal and external validity. The questionnaire is completed by the mother. Time: 15 minutes.

2.2 Childbearing Attitudes questionnaires (CAQ).

The Childbearing Attitudes Questionnaire (CAQ), assessed at 6 and 18 postpartum, is a 76-item scale concerning attitudes toward pregnancy and birth, self-esteem, and other interpersonal relationships. Items include 3-6 items for each of 19 different issues important to infants and childbirth, counterbalanced for direction to minimize response bias. Participants respond to each item on a 7-point scale from disagree strongly (1) to agree strongly (7). The attitude factors for the present study were derived from these items by factor analysis (Ruble et al., 1990). Attitude clusters assess 1) feelings of attachment towards her own infant (attachment), 2) feelings of nurturance towards infants in general (other infants), 3) feelings about caretaking activities, 4) feelings of adequacy in the maternal role (maternal adequacy), 5) feelings towards partner/spouse (relationship with partner) and 6) feelings towards their own mothers (relationship with mother). For the present study, we will use 4 subscales: maternal worries, maternal self-confidence, identification with pregnancy, and feelings about children (20 items total). Time: 7 minutes.

- **Twelve-month home interview: First visit (90 minutes)**

Mother

1. Questionnaires

1.1 Interview: Same as described in the 6 months mother evaluation (See first visit, section 1).

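### The five money-problem items at the 6- and 12-month postpartum interviews look back to the start of pregnancy, so they mix prenatal with postnatal hardship and cannot serve as a dated postnatal stressor

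*Combined protocol and SAP*

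**What the plan says.** The items are in the Combined protocol and SAP, III. Methods, Six-month home interview: First visit, 1.1.4. The block opens: "Chronic stressors are assessed via measures of money problems, food security, housing problems, work stress, negative interactions with others and conjugal violence". The money part has five questions (housing, utilities, food, prescribed medicines, other needs) under the stem "Each woman is asked if, since the beginning of their pregnancy, they have lacked money to" pay for each of them.

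On timing, item 1.1.1 says "Maternal stress measures are assessed at 6 and 12 months postpartum". The twelve-month first home visit gives its content only by cross-reference: "Interview: Same as described in the 6 months mother evaluation (See first visit, section 1". No different recall window is given there.

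Other items in the same interview use a short window. For negative interactions (1.1.6): "The woman also indicates the number of times in the past two weeks that she has had a disagreement with each of these people". The social support needs in 1.3.1 also refer to the last two weeks.

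The Introduction states an interest in "interactions between prenatal and postnatal environmental conditions in predicting health outcomes". The Participants section says the project will draw on the "multivariate assessment of prenatal adversity in The Montreal Prematurity Study", so a separate source for the pregnancy period exists. Neither document gives a scoring rule for the money items or says how their answers are to be split between the two periods.

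**The concern.** The plan distinguishes adversity before birth from adversity after it. A question asked after birth but reaching back to the start of pregnancy does not respect that line. A mother who was short of money while pregnant and comfortable since must answer yes at both visits, exactly like a mother whose hardship began after the birth. The answer is also cumulative, so it can record hardship starting but never hardship ending.

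This matters in three places in the Combined protocol and SAP:

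- The recruitment text in III. Methods suggests that low socio-economic status, with its chronic stressors, may act through slow growth after birth rather than through growth restriction in the womb. Low-status, normal-weight babies are oversampled for that reason. Testing that route needs stressors dated after birth.
- II. Hypotheses makes mother-infant interaction depend on the mother's emotional well-being, and IV. Statistical analysis describes these measures as indicators of stress and as possible mediators and moderators of its effects on well-being.
- IV. Statistical analysis plans multilevel models of whether effects persist, followed by structural equation models.

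The Introduction also names maternal stress and malnutrition as major predictors of growth restriction. A pregnancy-only yes, for example to lacking money for food, may thus record a cause of the birth-weight grouping while being read as postnatal stress.

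**Working it through.** The plan gives no figure for this point, so there is none to reproduce. The check has three parts.

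**1. Prenatal share of the recall window.** Inputs: the start of the window (1.1.4), interviews at 6 and 12 months (1.1.1), and gestation above 37 weeks (Participants). Share = length of pregnancy / (length of pregnancy + time since birth).

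- In months, taking pregnancy as 9: 9/(9 + 6) = 9/15 = 60%; 9/(9 + 12) = 9/21 = 43%.
- In weeks, for 37 to 40 weeks of gestation: 37/63.1 = 58.6% to 40/66.1 = 60.5% at six months; 37/89.2 = 41.5% to 40/92.2 = 43.4% at twelve.

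These are shares of calendar time, not of bias.

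**2. Share of yes answers that are prenatal only.** Let p be the prevalence of hardship, taken as equal in the two periods, and φ the correlation between them. The documents give neither; both are assumed.

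- P(both) = p² + φp(1 − p)
- P(either) = 2p − P(both)
- Prenatal-only share = [p − P(both)] / P(either)

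Example with p = 0.2, φ = 0.5: P(both) = 0.04 + 0.5 × 0.16 = 0.12; P(either) = 0.40 − 0.12 = 0.28; share = 0.08/0.28 = 29%.

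**3. Loss of a purely postnatal effect.** Nobody who answers no has postnatal hardship, and a fraction p/P(either) of those who answer yes do. If prenatal hardship has no effect of its own, the slope on the item is p/P(either) times the true postnatal effect. In the example, 0.20/0.28 = 71%.

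| p | φ | P(either) | prenatal-only share of yes | slope retained |
|---|---|---|---|---|
| 0.1 | 0 | 0.190 | 47% | 53% |
| 0.1 | 0.3 | 0.163 | 39% | 61% |
| 0.1 | 0.6 | 0.136 | 26% | 74% |
| 0.2 | 0 | 0.360 | 44% | 56% |
| 0.2 | 0.2 | 0.328 | 39% | 61% |
| 0.2 | 0.3 | 0.312 | 36% | 64% |
| 0.2 | 0.5 | 0.280 | 29% | 71% |
| 0.2 | 0.6 | 0.264 | 24% | 76% |
| 0.2 | 0.7 | 0.248 | 19% | 81% |
| 0.3 | 0 | 0.510 | 41% | 59% |
| 0.3 | 0.3 | 0.447 | 33% | 67% |
| 0.3 | 0.6 | 0.384 | 22% | 78% |

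Over these combinations the prenatal-only share runs from 19% to 47%, and the retained slope from 53% to 81%. If prenatal hardship does affect the outcome, the item picks up that effect too and the slope is no longer simply attenuated.

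**What can still be dated.** A no at six months followed by a yes at twelve places the hardship in months 6 to 12. A no at either visit rules out hardship up to that visit. A yes at six months cannot be placed, and the twelve-month answer adds nothing for that mother.

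**The case against.** A reader might infer that the study cannot separate the two exposures whose interaction it tests. The documents do not support that. II. Hypotheses sets fetal adversity against the postnatal environment, chiefly mother-infant interaction. The prenatal side is grouped by birth weight, and mother-infant interaction is observed by video, a maternal-behaviour Q-sort and the strange situation. The 72-month Protocol (Analyses, Hypothesis 1) tests birth weight for gestational age by secure or insecure attachment. The power analysis in the Combined protocol and SAP uses maternal sensitivity and infant cortisol. None of these uses the money items.

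A reader might also speak of a contaminated postnatal stress score. No such score is defined. Money problems are one of six named chronic-stressor domains, beside separate perceived and parental stress scales.

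Nor is the group with prenatal but no postnatal hardship empty in general. It is empty only if money hardship is used on both sides of the interaction, with this item as the postnatal side. The plan does not state such an analysis, and with birth weight as the prenatal factor every cell can be filled.

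It is also fair to say that a long window can suit a chronic stressor, that the twelve-month wording is inferred from a cross-reference because the interview form is not in the documents, and that the parent study may hold matching prenatal items. All of this limits the scope, but it does not remove the defect. Even if the parent study asked the same questions, which is not stated, a mother who said yes in pregnancy must say yes again, so her postnatal state stays unknown. Prenatal assessment is described at 24 to 26 weeks, so a no then followed by a yes could still refer to late pregnancy.

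**Conclusion.** The point holds for the five money items. As written, at both 6 and 12 months, a yes mixes hardship before and after birth and cannot revert. The window shares of about 60% and 43% follow from the stem and the visit times. The 19% to 47% range for prenatal-only answers rests on assumed, equal prevalences and assumed correlations, and should be read as an illustration. The retained slope of 53% to 81% needs the further assumption that prenatal hardship has no effect of its own.

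The consequence is misclassification wherever money hardship is treated as a postnatal exposure: the postnatal pathway proposed for socio-economic status and chronic stressors, stress as a predictor of maternal well-being and care, and the longitudinal and structural equation models. The main interaction tests and the powered analysis stand. The documents do not show whether the parent study asked the same items, or whether the shortened 24-month interview keeps them. Severity is minor to moderate.

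**What to change.** Change the stem to *since your baby was born* at 6 months and *since our last interview* at 12 months, and also at 24 months if the short version keeps the items. Take the pregnancy period from the parent study where it is available. If a cumulative measure is wanted, derive it by combining waves: dated answers can be added up, but a cumulative answer cannot be taken apart.

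Before fielding, this is one phrase in the interview form. The small price is that the items no longer match earlier uses of the same stem word for word.

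The 72-month Protocol reports that the maternal interview had by then been given at 6, 12, 24, 36, 48 and 60 months, so rewording cannot repair those waves. For answers collected under the present stem, the analysis plan should label the items cumulative since the beginning of pregnancy and exclude their use as postnatal-only predictors. That costs a sentence in the plan and gives up only analyses that the items cannot support.

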1.2. Resilience

The three core measures of personal resilience are self-esteem, optimism and beliefs about control. In addition, just world beliefs, life changes, motives for maternal caregiving (maternal care regulation), and commitment (willingness to sacrifice) are assessed.

1.2.1. Personal Resilience. Self-esteem is assessed using the short form (4 items) of the Rosenberg Self-Esteem Scale (Major et al., 1998), the most widely used instrument to assess self esteem (Rosenberg M., 1965; Vallières and Vallerand, 1990).

1.2.2 Optimism is assessed using a short form of the Life Orientation Test (Scheier and Carver, 1985). The full scale has good internal consistency, ($\alpha = .76$) and good test-retest stability (.79). The short form we are using includes all 8 items from the original scale and deletes the four filler items.

1.2.3 Beliefs of control is assessed using the 7 items mastery beliefs scales (Pearlin and Schooler, 1978).

1.2.4 Life changes. This is an open-ended question at the end of the interview that elicits qualitative data from the woman. "Sometimes after having a baby, people think about life in a different way. In what ways, if any, do you think about life differently now?" The woman's response is tape recorded and transcribed.

1.2.5 Belief in a just world. Theoretical and empirical work has suggested that this represents a core belief that is fundamentally challenged by major negative life events. A prospective study of coping with the loss of a spouse found that a belief in a just world buffered the effects of spousal loss on psychological distress (8 items) (Bonanno et al., 2002).

1.2.6 Maternal care regulation. This is derived from self determination theory (Deci and Ryan, 1991) and corresponds with the work of one of the team members showing that the motivational bases for caregiving was associated with caregiver well-being among those caring for a loved one with Alzheimer's. The idea is to differentiate between caregiving driven by guilt vs. more self determined motives for caregiving (8 items). The latter type should be more nurturing and promote greater autonomy in the child.

1.2.7 Sacrifice scale. These three questions measure the extent to which a woman is having to sacrifice other things for caregiving. It is an indicator of commitment to the caregiving relationship.

1.3. Social resources:

1.3.1 Social support is assessed with five items from the ASSIS (Barrera M., 1981). This assesses private feelings, material aid, advice, positive feedback, and physical assistance. The social participation domain (have fun or relax with) was not assessed. Included are questions assessing the number of people available "in time of need" and to "confide in or talk freely about your problems." It then assesses whether the woman has needed support in the past two weeks in each of the five areas specified above. For each need, the woman is then asked if she received help, and if not, how many times she was left without anyone to help her in this way.

1.3.2. Relationship quality is assessed with the six item Quality of Marriage Index (Norton R., 1983). The QMI has been found comparable to the Dyadic Adjustment Scale (DAS), correlating with the DAS at .90 (Heyman et al., 1994). Moreover, one of the items in the QMI (and retained in our study) is Magical Question 31 from the DAS. That is the question that correlates with the other 31 items of the 32-item DAS at .70 (Goodwin R., 1992). In addition, the one-item Inclusion of Other in Self Scale is given to

assess the degree of relationship closeness. Finally, the McGill Assessment of Relationship Commitment ([name] and Gagné) is assessed. In total, 11 questions are administered to assess relationship quality.

1.3.3. Attachment is assessed with items from Brennan and colleagues' comprehensive review and distillation of the most commonly used measures of adult attachment (Brennan et al., 1998). Their analysis of responses from 1,076 respondents generated two subscales representing the two theoretical dimensions of adult attachment: avoidance of closeness and anxiety about relationships. Earlier versions of attachment measures included measures of both fear of closeness and fear of dependency. Because both of these fold into the avoidance of closeness measure, four items loading on this subscale were chosen (2 fear of closeness and 2 fear of dependency items). Because anxiety has stood alone as a measure even in earlier versions, only three items with the highest factor loadings for this subscale were retained. We have successfully used this 7-item measure in a series of three experiments (Bartz and [name], 2003).

1.3.4. Parental Bonding Inventory (PBI, Parker et al., 1979) is a standard in retrospective assessment of parental educational style (48 items) (Parker and Lipscombe, 1980).

1.4. Health Behaviors:

Health Behaviors are taken at 6, 12, 24 and 36 months post-partum using a 9 items questionnaire. Questions assess cigarette smoking, use alcohol, prescribed medications and non-medicinal drugs ("recreational" or "hard" drugs). Breastfeeding will be assessed at 6 and 12 months.

1.5. Depression:

Maternal depression measures are taken at 6, 12, 24 and 36 months postpartum. The Center for Epidemiological Studies, Depression Scale (CES-D) is a 20-item instrument that has excellent internal consistency (.90) and reasonable test-retest reliability (.54) for a scale that should be sensitive to adverse changes in the respondent's environment (Radloff 1997; Fuhrer & Roullion 1989). For the current project, the scale is being used primarily as a continuous measure of change in depression (from the prenatal interview to the one year post partum interview). Although there are cutoff points for classification purposes, caution is needed to avoid a high false positive rate (Santor et al. 1995). These mood factors are reliable and valid for the post-partum population and show consistency across time, (Fleming et al., 1988,1990). Correlations between the current experience scale (CES) and standardized mood scales (e.g. the MAACL, Zuckerman, 1985 and the BDI, Beck et al.,1961) are highly significant (range .55 to .80; Fleming et al.,1988,1990).

Six-month home interview: Second visit (Time: 60 minutes)

Mother

1. Basal salivary cortisol:

Maternal basal cortisol levels are assessed over the diurnal cycle using salivary samples obtained at 0800, 0830, 1000, 1200 (with the sample taken prior to lunch), 1600, 1800 and 2200 hours. The samples will be taken over two consecutive days using salivettes at 6, 12, and 24 months postpartum. The samples, which are stable at room temperature for 3-4 days, will be collected by the subject over the course of their normal daytime activity using portable PalmPilot devices as prompts to ensure accurate sample collection. The subject will be asked to enter the exact time in the recorder. Samples will be collected and processed for radioimmunoassay in [name]'s lab, which has considerable experience with salivary hormone assays (e.g., [name] et al. 1998, 2002). Time: 2 minutes.

2. Home environment evaluation

Household observations checklist/ household satisfaction index.

The household observations checklist is completed by research assistant immediately following home visit and the household satisfaction index requires research assistant to ask specific questions of mother. Both measures provide a basis for understanding the nature of the home setting. The "household observations checklist" is largely extracted from household assessment guides used in other studies. Responses to Questions 1-5 relate to socio-economic position; responses to Question 6 will be key in relation to subsequent neighborhood level surveys. The literature base for Q1-6 is housing and urban planning.

The "household satisfaction index" derives from epidemiological, health sciences and urban studies research. This literature establishes a link between perceived satisfaction with housing and infant respiratory problems and residents' emotional/affect and behavioural measures. Items given here have "good" Cronbach's alpha (better than 0.65, quite high for this literature) and demonstrated utility in relation to health status, broadly defined. Time: 2 minutes.

Infants

1. Questionnaires

Health of the baby and breastfeeding questionnaire

This 30 items questionnaire will be assessing the health of the infant since his birth and also breastfeeding. For the most part, these are yes/no questions. Time: 7 minutes.

2. Standardized assessment and experimental tasks

Psychomotor Development. The Bayley Scales of infant Development (BSID II, Bayley, 1993) are administered at 6, 12 and 36 months. This 1993 revision of the most widely used infant development assessment consists of three scales: the Mental Scale and Motor Scale assess current level of cognitive, language, personal-social, fine and gross motor development; the Behavior Rating Scale assesses behavior during testing. The BSID II is appropriate for 1 to 42 months of age. Normative data were updated in 1993 and data are available for children with Down syndrome, prematurity and prenatal drug exposure. The assessment is conducted by a trained individual and takes 30 minutes at 6 months and 45 minutes at 12 and 36 months. Training for the Bayley assessment is supervised by [name], from the "Laboratoire d'étude du nourrisson" at Université du Québec à Montréal.

3. Mother-infant interactions (behavioral observations)

Videotaped Mother-Infant Interaction. Once questionnaires are completed, the researcher sets up equipment for a 20-minute video of mother-infant interactions and takes baseline salivary samples from mother and baby (see below). During the video, mother and infant are alone in the room. Upon completion of the video, at 20 and 40 minutes after the start of the interaction, the researcher takes the second and then third saliva sample.

Observations: Infants are given the opportunity to feed and be changed prior to the video. Mothers are seated on a comfortable stationary chair/sofa and asked to interact as they would if alone with the infant but to remain within the camera's view and not to feed the infant. Behaviours are later coded from videotape using the BEST system. The coded behaviours on each occasion are adjusted to the age of the infant. For example, at 6 months they include attending to baby (enface, looking over baby), affectionate contact (affectionate burping, stroking, poking or hugging), in proximity to infant (with nose within 2 cm on infant's body), vocalizing to infant (talking or singing to infant), and instrumental activities (instrumental burping,

wiping face, adjusting blanket), and infant activities (hands waving, squirming, feet waving, crying, vocalizations).

Inter-observer reliability is estimated by having two independent observers code 6 to 10 videotapes. In prior studies, percent agreement ranged from 70% to 100% for different behaviors.

4. Salivary cortisol

Basal salivary samples are taken at two time points over the day. Saliva will be collected by swabbing the child's cheek with cotton applicator (Q-tips). Once wetted, the Q-tip is placed in a plastic eppendorf. The eppendorf is then stored at -20°C. Samples are taken at 0800h (AM) and at 1600h (PM), for two consecutive days at 6, 12, and 24 months of age. These samples will be coordinated with the maternal samples using the PalmPilot probes that provide cues for sampling for the mother. Only two samples are taken from the children because of the difficulty posed by daycare sampling. Salivary samples will be analyzed in the [name] lab using radioimmunoassay procedures that are routine for this group.

- **Six-month laboratory visit (25 minutes)**

Infants

1. Standardized assessment and experimental tasks

1.1. Attention/Impulsivity.

These tasks are laboratory-based experimental tasks designed for infants. Because abilities of infants change dramatically over the first few years, most cannot be used across ages. Instead, we use analogous tasks to tap the same abilities. At 6 and 18 months the infant is in a curtained enclosure, in an infant seat or highchair, or on mother's lap, facing a display of three monitors (Fig. 2). For a given task all or only some of the monitors are used. A peephole in the center allows a camera to film the infant's face so that gaze can be scored from the resulting recording. At 36 months the infant is seated at a low table facing the experimenter.

1.1.1. Habituation of visual attention (6 months). This is one of the few paradigms applicable to assess attention control in very young infants. The basic paradigm involves repeated presentation of a stimulus. With repetition, attention normally decreases and the rate of decrease reflects ability to take in and organize information. The rate of decreased attention as well as patterns of attention (e.g. number of looks in a trial, duration of discrete

looks) are related to later cognitive abilities (see Fagen & Ohr, 2001 for a review). Typically, to ensure that attention decrease is specific to the stimulus (i.e., not a result of fatigue) a novel stimulus or modification of the original is presented at the end of the habituation sequence. Many forms of this paradigm with variation in similarity and dimensions of change for the habituated and novel stimuli are used to study questions about infant cognitive abilities. In the present study, two sets of stimuli are used with all trials appearing on the central monitor. In one, five brightly colored stationary fish appear, all facing in the same direction for 8 trials of 15 second each, with three seconds between trials. On the 9th trial the same fish are presented facing in the opposite direction. The other sequence presents a schematic face that changes orientation (upside down) on the novel trial. Measures are based on change in 1) total looking over trials, number of looks per trial, and duration of longest look on each trial. Time: 10 mins.

1.1.2 Visual Expectation Paradigm, (Haith, Hazan, & Goodman, 1988, 6 and 18 months) Learning of context dependent sequences requires development of the frontal structure underlying ability to guide behavior using new information available in the context and to inhibit old responses (Clohessy, Posner and Rothbart, 2001). Visual expectation tasks are a classic measure of this type of learning. In our version of the visual expectation paradigm, a single computer-generated stimulus is presented on one of the three monitors according to predetermined sequences, until the infant orients to it (Interstimulus interval = 600 milliseconds). *Simple sequences* have a repeating pattern in which associations between target locations are unique. Each event reliably predicts the next in the sequence. (e.g., 1-2-1-2-1-2). *Complex sequences* have a repeating pattern in which *some* events reliably predict the next target location but others do not (e.g., 1-2-2-1-2-2-1). Infants as young as 3 months learn to anticipate this latter complex sequence (Canfield & Haith, 1991). The presented stimuli are either colorful looming shapes that alternate between squares and diamonds, or human faces alternating between neutral and angry expressions. Six-month-old infants see sequences that use only the lower two monitors; 18-month-olds see sequences using all three monitors. The measures derived are: 1) the number of correctly anticipated trials; 2) latency to anticipate or respond to an image on correct trials and 3) the difference between the number of correctly anticipated trials in the complex sequence and the simple sequence. Time: 10-15 mins (longer for the older group).

2. Questionnaires

The mother will fill out questionnaires about her child while he/she is undergoing evaluation.

2.1. Temperament.

Although there are laboratory-based observational procedures for assessing infant temperament (e.g., Goldsmith & Rothbart, 1996) these are labour intensive and therefore not as widely used as parent report instruments. The Infant Behavior Questionnaire, Revised Version (IBQ, Garstein and Rothbart, 2003) is completed at 6 and 12 months and the toddler version at 36 months. This is a widely used parent-report measure of infant temperament. The items represent 14 scales but factor analysis reveals three primary factors: a) impulsivity, b) negative affectivity and c) effortful control. We chose this instrument, partly because of interest in impulsivity as a key outcome variable and partly because this measure is well researched and has internal and external validity. The questionnaire is completed by the mother. Time: 15 minutes.

2.2 Childbearing Attitudes questionnaires (CAQ).

The Childbearing Attitudes Questionnaire (CAQ), assessed at 6 and 18 postpartum, is a 76-item scale concerning attitudes toward pregnancy and birth, self-esteem, and other interpersonal relationships. Items include 3-6 items for each of 19 different issues important to infants and childbirth, counterbalanced for direction to minimize response bias. Participants respond to each item on a 7-point scale from disagree strongly (1) to agree strongly (7). The attitude factors for the present study were derived from these items by factor analysis (Ruble et al., 1990). Attitude clusters assess 1) feelings of attachment towards her own infant (attachment), 2) feelings of nurturance towards infants in general (other infants), 3) feelings about caretaking activities, 4) feelings of adequacy in the maternal role (maternal adequacy), 5) feelings towards partner/spouse (relationship with partner) and 6) feelings towards their own mothers (relationship with mother). For the present study, we will use 4 subscales: maternal worries, maternal self-confidence, identification with pregnancy, and feelings about children (20 items total). Time: 7 minutes.

- **Twelve-month home interview: First visit (90 minutes)**

Mother

1. Questionnaires

1.1 Interview: Same as described in the 6 months mother evaluation (See first visit, section 1).

